
Patients diagnosed by the LRTC with PTSD, receiving evidenced based combined pharmacological and psychotherapy (either PE or CPT)
	
 1) Male or female English-speaking active duty or recently retired veteran patients who have deployed post 9/11 receiving treatment at LRTC between the ages of 18-65 years; 2) Patients must have a diagnosis of PTSD confirmed by the Clinician-Administered PTSD Scale (CAPS-5) at screening, 3) Subjects must have a minimum PTSD Symptom Checklist for DSM-V (PCL-5) symptom severity rating of 25. 	
 1) Subjects with a diagnostic history of bipolar disorder, schizophrenia or schizoaffective disorder as documented in the medical record. 2) Substance use disorder during the 12 months prior to screening; except that Mild - Moderate, but not Severe, Alcohol Use Disorder (using DSM-5 criteria) will be allowed as determined by LRTC medical provider review. 3) Any history or signs of serious medical or neurological illness including seizure disorders. Except for seizures, a subject with a clinical abnormality may be included only if the study clinician considers the illness will not introduce additional risk and will not interfere with the study procedures. This will be determined during the screening phase via self-report and/or medical history review. 4) History of traumatic brain injury (TBI) with loss of consciousness for 20 minutes or more as determined by the History of Head Injuries questionnaire. 5) Females will be excluded if they are pregnant (i.e. positive pregnancy test identified after their LRTC intake). 6) Any history or signs of metal objects deemed unsafe for MRI or that may adversely affect image quality of the brain region (e.g. surgical clips, cardiac pacemakers, metal implants, etc.) in the body at the time of screening as indicated by self-report. MRI can have risks for persons with foreign bodies implanted in their body.

Item 6
Research Plan / Description of the Research Methods a. *Provide a comprehensive narrative describing the research methods.*
Provide the plan for data analysis (include as applicable the sample size calculation).

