Step-by-Step Methods: We propose to test 100 patients (i.e. 50 per arm) who meet criteria for PTSD as determined by the Clinician Administered PTSD Scale (CAPS-5) and the outlined study inclusion criteria. We anticipate consenting and screening approximately 200 male and female subjects, in order to meet the target enrollment goals. To account for subject dropouts and retain a sample of 100 subjects completing the double-blind treatment phase (50 per treatment group), 132 eligible subjects (66 in each group) meeting the study inclusion criteria will be randomized for the study. See also Table of Study Procedures below.

Recruitment

Patients will be recruited at LRTC from institution's PTSD inpatient program by the study staff supervised by the On-site Investigator's team. Upon admission to the LRTC, patients will be informed about this treatment trial by either their staff psychiatrist or a member of the LRTC's research team. Each patient will be given an information sheet describing the study. If interested in participating, each patient will be shown a video describing the treatment trial and each of the tools/treatments used throughout the study (i.e. MRI and TMS).

Pre-Screening and LRTC Intake

Under an IRB approved HIPAA Waiver of Authorization, Waiver of Informed Consent, and Waiver of Documentation of Informed Consent, study personnel will conduct a brief pre-screening intake interview where the basic study inclusion and exclusion criteria will be reviewed to help the individual determine if he or she meets the study criteria or has obvious exclusions from the study protocol. This information will be maintained as a secure file with the following information: name, phone number, name of study, referral date, referral source, potential eligibility status, reason if not eligible, and verbal permission to contact the caller in the future for other studies. Subjects who agree to study participation will sign a consent document before any further screening will take place. Any individually identifiable information and Protected Health Information (PHI) collected on individuals who do not consent to participation will not become part of the research data. If subjects agree to participate in the research, the identifiable data collected will become part of the subjects' research records and will be stored according to the research confidentiality plan.

Consent Process

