Clinical Outcomes Data Analysis plan. All pre-treatment and post-treatment MRIs will be acquired and analyzed at the RII, however, all of the statistical analysis of the symptom scores for this project will be done upon completion of recruitment and termination group blinding. The primary efficacy outcome measure will be the PTSD Checklist (PCL-5) for symptoms assessed pre-treatment, weekly during treatment, post-treatment, and 1-month following the completion of treatment and the Clinician-Administered PTSD Scale for DSM-5 (CAPS-5) for the diagnosis of PTSD assessed pre-treatment and 1-month following the completion of treatment. The primary analysis will use mixed effects regression models. Secondary analysis will focus on changes in PTSD symptoms clusters, effects of the intervention in mood symptoms, functioning and cognitive outcomes. Types and rates of adverse events will be summarized and compared across the study groups. The durability of benefit and the clinical significance of PCL changes will be explored. Non-compliance to protocol as defined as missing two consecutive iTMS sessions or receiving less than 16 iTMS sessions during hospitalization at LRTC will be assessed for and evaluated in data analysis.

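### The primary PCL-5 mixed model states no baseline adjustment; a common-baseline or baseline-adjusted form would be at least as precise in large samples for about one degree of freedom.

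*Combined protocol and SAP*

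**What the plan says.** The clinical outcomes plan is one paragraph at the end of Item 6, under Data Analysis. It defines the first primary measure and its schedule: "The primary efficacy outcome measure will be the PTSD Checklist (PCL-5) for symptoms assessed pre-treatment, weekly during treatment, post-treatment, and 1-month following" the end of treatment. CAPS-5 is the second, named "for the diagnosis of PTSD assessed pre-treatment and 1-month following the completion of treatment". The method is one sentence: "The primary analysis will use mixed effects regression models". No fixed effects, covariates, covariance structure, treatment contrast or primary visit are given, and baseline adjustment is not mentioned anywhere else in the document.

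Two inclusion criteria in Item 5 bear on the point. For PCL-5: "Subjects must have a minimum PTSD Symptom Checklist for DSM-V (PCL-5) symptom severity rating of 25". For CAPS-5: "Patients must have a diagnosis of PTSD confirmed by the Clinician-Administered PTSD Scale (CAPS-5) at screening". The Table of Study Procedures schedules both instruments at baseline. On size, Item 6 says "We propose to test 100 patients (i.e. 50 per arm) who meet criteria for PTSD", and that "132 eligible subjects (66 in each group) meeting the study inclusion criteria will be randomized for the study".

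**The concern.** Pre-treatment is listed as one of the occasions on which the outcome is measured, and nothing is said about using it as a covariate. The common default for such data puts every occasion in as an outcome row, with arm, time and arm-by-time as fixed effects and a separate baseline mean for each arm. The treatment effect at a visit is then the difference between arms in change from baseline. This ignores the fact that randomisation makes the two baseline means equal in expectation, and it can give away precision.

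The trial plans 50 completers per arm and states no power, so there is no sign of precision to spare. The Random Assignment section describes no stratification by severity. At 50 per arm the baseline difference has a standard error of √(2/50) = 0.20 SD, so some chance imbalance is to be expected. The plan also places the symptom-score analysis after group blinding ends. Baseline handling that is still open then could be chosen with the arms known.

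**Working it through.** **Plan's own figure.** The sample size cannot be rebuilt, because alpha, power, effect size and SD are all absent. Going from 132 randomised to 100 completers implies dropout of 1 − 100/132 = 24.2%; no rate is stated. The ratios below do not depend on n.

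**Inputs.** Two arms of equal size (Item 6). Baseline PCL-5 is available in everyone (Item 5 and the procedures table). Two quantities are assumed because the documents omit them: r, the baseline-to-follow-up correlation, taken as 0.3, 0.5 and 0.7; and k, the baseline SD divided by the follow-up SD, taken as 1 and 0.7. A k below 1 is plausible because entry cuts the PCL-5 range at 25.

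**Formulas.** Variance of the arm contrast at one follow-up visit, in units of 2σ²/n, with σ the follow-up SD:

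- unadjusted post-treatment difference: 1
- difference in change: 1 + k² − 2rk, which is 2(1 − r) when k = 1
- baseline as covariate, or common baseline mean: 1 − r²

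The second minus the third is k² − 2rk + r² = (k − r)². This is never negative and is zero only when k = r. So in large samples the change contrast is never the more precise of the two.

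**Results.**

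| | r = 0.3 | r = 0.5 | r = 0.7 |
|---|---|---|---|
| Adjusted, 1 − r² | 0.91 | 0.75 | 0.51 |
| Change, k = 1 | 1.40 | 1.00 | 0.60 |
| Ratio adjusted/change, k = 1 | 0.65 | 0.75 | 0.85 |
| Cut, k = 1 | 35% | 25% | 15% |
| Change, k = 0.7 | 1.07 | 0.79 | 0.51 |
| Ratio adjusted/change, k = 0.7 | 0.85 | 0.95 | 1.00 |
| Cut, k = 0.7 | 15% | 5% | 0% |
| Cut against post-treatment difference, r² | 9% | 25% | 49% |

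At any fixed alpha and power the detectable difference scales with the square root of the ratio. For k = 1 that is √0.65 = 0.81, √0.75 = 0.87 and √0.85 = 0.92, so it shrinks by 19%, 13% and 8%.

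**Check on the repeated-measures design.** Generalised least squares was run on five visits (baseline, weeks 1 to 3, 1 month) with complete data and equal SDs, under compound symmetry and under an autoregressive-type correlation. The unconstrained change contrast at the last visit gave 1.40, 1.00 and 0.60. The model that keeps baseline as an outcome but gives both arms one baseline mean gave 0.91, 0.75 and 0.51, identical to covariate adjustment.

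**Cost of adjustment.** One covariate inflates the variance by about (N − 3)/(N − 4) = 97/96 = 1.010 at N = 100. Against the unadjusted post-treatment difference, adjustment breaks even at |r| = √(1 − 96/97) ≈ 0.10.

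**The case against.** The strongest reply is that the plan does not adopt the less precise method; it adopts no particular method. The list of occasions describes when PCL-5 is measured, not which rows enter the model. A reader might infer that the pre-treatment score serves only as an outcome time point, but the text neither says so nor excludes a covariate. This stands, and it makes the loss conditional on how the model is fitted.

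Keeping baseline as an outcome is also not the fault in itself. With a common baseline mean the precision equals that of covariate adjustment. The loss comes only from leaving the baseline means free and reporting change.

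A reader might also infer that the CAPS-5 analysis is a pure change-score test, since it has two occasions. The documents do not support this. The plan names CAPS-5 for diagnosis, and every participant has the diagnosis at entry, so baseline diagnosis is a constant with nothing to adjust for. The linear variance formula does not apply to a binary outcome, and in a logistic model adding a covariate changes the odds ratio being estimated. The argument reaches CAPS-5 only through the 0-80 severity score.

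Finally, the size is uncertain. It rests on r and k, and the gain vanishes when k = r. A slope or an average over visits would give other ratios, and no contrast is named. Dropouts' partial data would also enter a mixed model, whereas the check above assumes complete data. All of this stands.

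It does not follow that nothing needs doing. The change contrast is the usual product of the model named, the adjusted form is no worse in large samples, and adjustment also helps if an unadjusted post-treatment comparison was intended.

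**Conclusion.** The point holds for PCL-5 as a conditional loss of precision. The plan states no baseline adjustment. Fitted in the usual unconstrained way, its model would have a variance above the attainable one: adjustment would cut it by 15% to 35% for equal SDs and r of 0.7 to 0.3, and by 0% to 15% if the baseline SD is 0.7 of the follow-up SD. Against an unadjusted post-treatment comparison the cut is 9% to 49%. If the sponsor already intends a common baseline mean or a baseline covariate, the gain is zero and only the wording is missing.

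Both approaches are unbiased under randomisation, so validity is not at stake. It is tempting to turn the ratio into extra patients or a gain in power. The documents do not support that: they give no power, effect size, SD or correlation to start from. Nor is adjustment strictly free. It costs about 1%, so in the limiting case k = r it would be marginally worse than the change contrast at this sample size.

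**What to change.** Specify the PCL-5 primary model as a constrained longitudinal model: categorical visit, one baseline mean common to both arms, arm-by-visit terms at post-baseline visits only, and unstructured covariance. Equivalently, model the post-baseline visits with baseline PCL-5 and baseline-by-visit as covariates. Name the visit at which the arm contrast is the primary result, and fix all of this before group blinding ends.

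State whether CAPS-5 is analysed as severity or as diagnosis. If severity, use the same form with the baseline severity score. If diagnosis, specify a separate model for a binary outcome at follow-up. Before naming its visit, reconcile the CAPS-5 timing: the instrument description in Item 6 places the second interview at the end of the intervention, while the analysis paragraph places it at 1 month.

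The cost is a few sentences in the plan and roughly one degree of freedom. No new data are needed.
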